Regarding diagnosis, in the first instance, it is advisable to perform a standard loaded radiograph of the foot to visualize any enthesopathy and peri- and intra-tendinous calcifications. It is also advisable to perform a musculoskeletal ultrasonography and as a second-level investigation an MRI, in order to visualize optimally the soft tissues and thus a tendon degeneration, although signs of tendon degeneration are not always accompanied by a positive clinical picture, either in the acute or subacute phase.

We can distinguish conservative and nonconservative treatments.

Conservative treatments include: exercise in an eccentric regimen as recommended by the 2010 "American Physical Therapy Association" guidelines (Grade A) [4]; focused shock wave physical therapy as suggested by the recent study by "Chimenti et al. " of 2017 (Grade B) [1]; the use of nocturnal splints,

on the other hand, does not present sufficient evidence to justify their use; corticosteroid and platelet-rich plasma (PRP) infiltrations, although frequently used in clinical practice, are not supported by solid scientific evidence.

In the literature, by contrast, we recall the 2012 study by Monto RR. who reports the satisfaction of 28 out of 30 patients with achilles tendinopathy treated with PRP ^[5] and several other Authors who have gained experience in this regard ^[6;7;8;9;10;11]. The use of SVF adipose stromal fraction in the treatment of tendinopathies is still being studied ^[12;13].

Non-conservative treatments include various surgical approaches, which may involve more complex tendon transfer surgeries, such as transposition of the long flexor hallux, or simpler scarification approaches; minimally invasive endoscopic approaches; or percutaneous echo-guided procedures, all of which currently lack sufficient scientific support.

Conservative treatment alone is often found to be unsatisfactory in 40% of cases, while proposed traditional and minimally invasive surgical treatments (such as scarifications) have mixed results and are not always reproducible in the literature.

In light of this, there appears to be a clear need to find minimally invasive therapeutic alternatives that can guarantee to achieve better results than the current ones in the early treatment of acute and subacute insertional and noninsertional achilles tendinopathies.

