3.14. Criteria of effectiveness

3.14.1 Primary Endpoint

The primary end point will be assessed at T8s/FU and will involve:

- Assessment of the VISA-A questionnaire score at time T8w/FU compared to time T0. A difference between the two groups of 12 out of 100 points on the questionnaire can be considered clinically significant [17].

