3.14.1. Secondaries End Points

- Evaluation of VISA-A score at time T3w and T6w/FU compared to time T0
- Assessment of the VAS score at time T3w, T6w/FU and T8w/FU compared to time T0
- Evaluation of the SF12 questionnaire at time T3w, T6w/FU, and T8w/FU compared to time T0.
- Evaluation of the fraction of subjects in each group achieving Minimal Clinical Disease (MCD) considering that the MCD of the VISA-A questionnaire is 18.5 (90% MCD).
- Assessment of analgesic drug unit consumption based on clinical diary at time T3w, T6w/FU and time T8w/FU (paracetamol 1000 mg. will be used as "rescue dose" in case of onset/recurrence of pain).
- Evaluation of the fraction of subjects in each group who drop out early in relation to Adverse Events (AE/SAE/SUSAR).

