4. STATISTICS

4.14. Sample size

A one-covariance analysis for two arms of 28 subjects each, in which the covariate of interest differs by 12 units in its mean value between the two arms (compared with a null hypothesis of no difference), with a common standard deviation assumed to be 15 units, and an R^2 value assumed to be 0.2 has a

power of 90.75% in discriminating the established difference between mean values, using an F-test at a significance level of 0.05.

Assuming dropout patients to be 20% of the total, the inflated sample size of the protocol becomes 36 patients per arm.

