4.15. Plan of statistical analysis

The primary endpoint will be evaluated by Ancova, as described in the numerosity calculation.

Secondary endpoints will be assessed as follows: 1) the VISA-A score at time T3s and T6s/FU compared with time T0 with Anova at repeated measures between group and within group; 2) the VAS at time T3s, T6s/FU and T8s/FU compared with time T0 with Anova at repeated measures between group and within group; 3) the SF12 questionnaire at time T3s, T6s/FU and T8s/FU compared with time T0 with Anova at repeated measures or Friedman's test; 4) the fraction of subjects in each group reaching Minimal Clinical Disease (MCD) considering that the MCD of the VISA-A questionnaire is 18.5 (90% MCD) with Fisher's exact test; 5) the units of analgesic drug consumed according to the clinical diary at time T3s, T6s/FUs and time T8s/FUs (paracetamol 1000 mg will be used as "rescue dose" in case of pain onset/recrudescence) with Friedman's exact test; 6) the fraction of subjects in each group who drop out of the investigation early in relation to Adverse Events (AE/SAE/SUSAR) with Fisher's exact test.

Statistical significance will be assumed for $p < 0.05$, unless corrected for multiple testing.

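### For the secondary endpoints the plan does not name an A-versus-B contrast as the test of the device, and its within-group and Friedman tests against T0 cannot isolate the device effect

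*Protocol*

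**What the plan says.** The Protocol and the combined protocol and SAP carry the same text on this point.

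- Under the heading "3.14. Criteria of effectiveness", the VISA-A secondary endpoint reads "Evaluation of VISA-A score at time T3w and T6w/FU compared to time T0". VAS and SF12 are worded the same way. None of the three names a comparison between arms.
- Section 4.15 item 1 analyses "the VISA-A score at time T3s and T6s/FU compared with time T0 with Anova at repeated measures between group and within group". Item 2 analyses "the VAS at time T3s, T6s/FU and T8s/FU compared with time T0 with Anova at repeated measures between group and within group".
- Item 3 (SF12) allows repeated-measures ANOVA or Friedman's test. Item 5 (analgesic units) gives only Friedman's test.
- The significance rule is "Statistical significance will be assumed for $p < 0.05$, unless corrected for multiple testing". No correction is then specified, and no sentence ranks the between-group and within-group results.
- The primary endpoint is handled differently: "The primary endpoint will be evaluated by Ancova, as described in the numerosity calculation". Section 3.14.1 judges it against a 12-point difference between the groups.
- Section 3.12 gives both arms the same six-week eccentric programme. Section 2.1 describes this treatment as "exercise in an eccentric regimen as recommended by the 2010" guideline, Grade A. Section 3.6 requires VAS of at least 5 and VISA-A between 50 and 75.

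**The concern.** The trial asks what the injections add to exercise. Only a comparison of Group A with Group B answers that. Change from T0 in Group A mixes any device effect with the effect of exercise, natural recovery and, because entry is selected on symptom scores, possible regression to the mean. A significant within-group result is therefore not evidence for the device, and the plan does not say so.

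Two misreadings become possible in the report. One is that significant improvement in Group A is presented as effectiveness. The other is that a significant result in A beside a non-significant one in B is taken as a difference between arms. For analgesic use the gap is plainer: the only planned test does not compare the arms at all.

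**Working it through.** **1. The plan's own figure.** Inputs from section 4.14: 28 per arm, difference 12, SD 15, R² 0.2, "using an F-test at a significance level of 0.05".

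- Residual SD = 15 × √(1 − 0.2) = 13.42.
- Noncentrality = 28 × 12² / (2 × 13.42²) = 11.2, with 1 and 53 degrees of freedom.
- Power = 90.75%, exactly as stated.

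The inputs are thus read as the plan means them.

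**2. SD of change from T0.** The plan gives none, so two values are used.

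- 15, taking the plan's SD directly as the SD of change.
- 15.77, deriving it from R². If the covariate is baseline VISA-A, the correlation is √0.2 = 0.447, and 15 × √(2 × (1 − 0.447)) = 15.77. This applies SD 15 at every visit; the 50 to 75 entry window would probably make the baseline SD smaller.

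**3. Chance that Group A's own test is significant when the device does nothing.** Two-sided paired t-test at 0.05, noncentrality = m / (SD/√n), where m is the gain from T0 with exercise and time alone. The documents do not give m, so it is an assumed range. Example: m = 5, SD 15, n = 36 gives 5 / (15/6) = 2.0 and 49.4%.

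| Assumed gain m (VISA-A points) | SD 15.77, n = 28 | SD 15, n = 28 | SD 15.77, n = 36 | SD 15, n = 36 |
|---|---|---|---|---|
| 0 | 5% | 5% | 5% | 5% |
| 3 | 16.3% | 17.5% | 19.9% | 21.5% |
| 5 | 36.6% | 39.8% | 45.6% | 49.4% |
| 8 | 73.5% | 77.7% | 84.1% | 87.5% |
| 10 | 89.9% | 92.5% | 95.9% | 97.3% |
| 12 | 97.2% | 98.3% | 99.3% | 99.7% |

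The rates fall if visits are less correlated. At zero correlation the SD of change is 15 × √2 = 21.2, and with n = 28 the rate is 22.5% at 5 points, 48.6% at 8 and 67.2% at 10.

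**4. The same check as a repeated-measures ANOVA.** This used 20,000 simulated trials with VISA-A at T0, T3 and T6, identical arms, the T3 gain set to half the T6 gain, and equal correlation between visits. The time test within Group A is significant in 30% (n = 28) or 37% (n = 36) of trials at a 5-point gain, 64% or 76% at 8, and 84% or 92% at 10. The group-by-time interaction is significant in 4.7% to 5.3% at every gain.

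**5. Significant in A, not in B.** With identical, independent arms that each pass with probability p, this pattern has probability p(1 − p). The maximum is 0.5 × 0.5 = 25%. At m = 5, SD 15, n = 36 it is 0.494 × 0.506 = 25%. In the simulation it reached about 23%.

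**6. The other reading of items 1 and 2.** If the wording means one mixed ANOVA, with group as the between-subject factor and visit as the within-subject factor, there is no separate Group A test and steps 3 to 5 do not apply. The time effect then pools the two arms and still says nothing about the device. The group main effect averages in T0, where randomised arms should not differ. The term that answers the question is the interaction, which is not named.

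**7. Friedman's test.** It ranks the repeated visits within each subject and has no factor for arm. Choosing it in item 3, or following item 5 as written, leaves SF12 or analgesic use with no A-versus-B result.

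No rate is computed for VAS, because the documents give no SD for it.

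**The case against.** The strongest reply is that the plan never says a within-group result counts as success. The phrase about comparison with T0 can simply define the variable: the primary endpoint uses it too and is then judged on a difference between the groups. Items 1 and 2 name the between-group analysis first, and the wording may describe the two factors of one mixed ANOVA. The percentages above are power to detect a real change from T0; they become false-positive rates only if someone reads that change as a device effect.

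Much of this stands. A reader might infer that the plan gives within-group tests the same standing as the randomised comparison. No sentence does so; the plan merely fails to rank them. A reader might also infer that Group A would pass almost surely with a useless device. That needs an exercise-only gain of roughly 10 VISA-A points or more, which the documents do not supply. The 12 points in sections 3.14.1 and 4.14 are a between-arm difference, not an exercise gain. Regression to the mean cannot be sized either, and for VISA-A the two-sided entry window leaves even its direction open.

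The reply does not remove the gap. On either reading of items 1 and 2 the contrast that isolates the device is unnamed, and no reading of Friedman's test supplies one.

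**Conclusion.** The point holds for the secondary endpoints in items 1, 2, 3 and 5. The plan does not say that they are judged on the A−B difference, and some of its tests cannot show one.

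If a test in each arm is intended, a device with no effect would still leave Group A with a significant VISA-A change in about one trial in six to one in five at a 3-point exercise gain, and in about nine in ten or more at 10 points. This assumes SD of change 15 to 15.8 and 28 to 36 subjects per arm. The size depends mainly on the exercise-only gain, which is an assumption throughout. If one mixed ANOVA is intended, those rates do not apply, and the fault is the unnamed interaction.

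The primary between-arm ANCOVA at T8 is untouched, so the confirmatory result is not in question.

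**What to change.** - **4.15 items 1–3:** name the A−B difference as the only inferential test, either baseline-adjusted at each visit or as the group-by-time interaction. State which of the two is used.
- **4.15 items 3 and 5:** replace Friedman's test with a between-arm comparison, for example a rank-based test of change in SF12 by arm and of analgesic units by arm.
- **Within-arm changes from T0:** report means with 95% confidence intervals, without p-values, labelled descriptive.
- **3.14:** add that secondary efficacy endpoints are judged on the difference between Group A and Group B.
- Make the same edits in both documents.

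This is a change of wording and needs no new data or patients. The cost is that the sponsor gives up within-arm p-values.

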3.6. Inclusion Criteria

- Male and female subjects aged 18 to 70 years.
- Subjects with tendon pain for not more than 24 weeks;
- Subjects with clinically diagnosed and ultrasonographically confirmed. insertional/noninsertional/mystic tendinopathy;
- Subjects with a VISA A score between 50 and 75;
- VAS \geq 5;
- Subjects able to understand and answer the SF12 questionnaire.
- Subjects able to understand and sign the informed consent.

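### The secondary repeated-measures ANOVAs of VISA-A and VAS name no sphericity correction or covariance model, so their nominal 5% level may be modestly exceeded

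*Protocol*

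**What the plan says.** Section 4.15 of the Protocol sets out the secondary analyses, and the combined protocol and SAP repeats it word for word. Item 1 analyses "the VISA-A score at time T3s and T6s/FU compared with time T0 with Anova at repeated measures between group and within group". Item 2 analyses "the VAS at time T3s, T6s/FU and T8s/FU compared with time T0 with Anova at repeated measures between group and within group". Item 3 allows repeated-measures ANOVA or Friedman's test for SF-12 at the same visits as VAS. The criterion is "Statistical significance will be assumed for $p < 0.05$, unless corrected for multiple testing".

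The section mentions no sphericity test, no Greenhouse-Geisser or Huynh-Feldt correction, no covariance structure, and no error term for the visit-versus-T0 comparisons that section 3.14 lists as endpoints. It does not say that a correction will be left out; it is silent. VISA-A at T8 is the primary endpoint and is tested separately by ANCOVA.

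**The concern.** Univariate repeated-measures ANOVA uses one pooled within-subject error. Its time and group-by-time F-tests are exact only if every difference between two visits has the same variance. VISA-A has three time points (T0, T3, T6) and VAS has four (T0, T3, T6, T8), so the condition matters for both.

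There is a plain reason to doubt it. T3, T6 and T8 are two or three weeks apart, all fall after treatment has begun, and use the same instrument. They may well correlate more with each other than any of them does with T0. In that case the pooled error is too small for a change from T0 and too large for a change between follow-up visits.

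At stake is the error rate behind a claimed p < 0.05 on secondary efficacy endpoints. One of these is the pain score, and pain reduction is half of the stated purpose in section 3.2. Silence also leaves the choice of correction open until the data have been seen.

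**Working it through.** **Inputs from the documents.** From section 4.14: "two arms of 28 subjects each", difference 12, SD 15, R² 0.2, "using an F-test at a significance level of 0.05". From section 3.6: "Subjects with a VISA A score between 50 and 75" and a T0 VAS of at least 5.

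**Assumptions, not in the documents.** Normal data, complete cases, equal covariances in the two arms and no true group difference. The T0-to-follow-up correlation is √0.2 = 0.447. All follow-up pairs share one correlation ρ, varied from 0.447 to 0.9. The VAS SD is 2.

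**The plan's own figure.** Residual variance = 225 × (1 − 0.2) = 180. Noncentrality = (28/2) × 144/180 = 11.2. The F-test on 1 and 53 df then has power 0.9075, which matches the stated 90.75%. That figure concerns the ANCOVA and does not depend on sphericity.

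**Departure from sphericity, three visits.** Take T0 SD 7.2 (25/√12, a uniform spread over 50-75) and follow-up SD 15. Two within-subject variances matter:
- Between follow-up visits: L = 225 × (1 − ρ).
- T0 against the follow-up mean: A = (2/3) × [7.2² + 225 × (1 + ρ)/2 − 2 × 0.447 × 7.2 × 15].

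Then ε = (L + A)² / [2 × (L² + A²)], and ε = 1 means sphericity.
- ρ = 0.6: L = 90.0, A = 90.2, ε = 1.00.
- ρ = 0.8: L = 45.0, A = 105.2, ε = 0.86.
- ρ = 0.9: L = 22.5, A = 112.7, ε = 0.69.

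**Role of the entry limits.** With no compression (T0 SD 15) at ρ = 0.8, A = (2/3) × [225 + 202.5 − 201.15] = 150.9 and ε = 0.77. This is further from sphericity than the compressed 0.86. Truncating T0 at 50-75 within the model, which also lowers its correlation with follow-up to about 0.22, gives about 0.83. So compression eases the problem here; a high ρ drives it.

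**Simulated two-sided error, 28 per arm, T0 truncated at the entry limits, at least 20,000 trials per setting.**

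| Test | ρ = 0.7 | ρ = 0.8 | ρ = 0.9 |
|---|---|---|---|
| VISA-A group-by-time F, uncorrected | 5.1% | 6.0% | 6.8% |
| VAS group-by-time F, uncorrected | 5.6% | 6.3% | 8.0% |
| VISA-A change from T0, pooled error | 6.4% | 7.6% | 9.1% |
| VAS change from T0, pooled error | 7.4% | 9.5% | 12.6% |

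With Greenhouse-Geisser, or with each contrast's own variance, the rates are 4.6% to 5.1%. In runs with a fixed T0 SD of 7.2 against 15 later, the uncorrected time F-test behaves like the group-by-time test (four visits: 6.1% at ρ = 0.8, 7.8% at 0.9).

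**Lower correlations.** At ρ = 0.6 with T0 SD 7.2, the uncorrected group-by-time F-test is at 5.1% (three visits) and 4.8% (four). Pooled-error contrasts, with T0 truncated, are at 5.2% (VISA-A) and 5.7% (VAS). At ρ = 0.447 with T0 SD 7.2, those contrasts are conservative: 3.9% (three visits) and 3.2% (four).

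**Arithmetic check on the contrasts.** Three visits, ρ = 0.8, T0 SD 7.2: the true variance of a change from T0 is 225 + 51.84 − 96.55 = 180.3. The pooled error supplies L + A = 150.2. The ratio is 1.20, and 1.96/√1.20 = 1.79 corresponds to about 7.4% two-sided, as the fixed-SD simulation also gives.

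**Tests that do not need sphericity.** The between-group main effect, and contrasts tested on their own change scores, stayed at 4.8% to 5.2%.

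**The case against.** The case against making much of this is strong. The error rate depends on correlations among T3, T6 and T8 that the documents never state, and on an assumed VAS SD. At 0.6 the effect has gone. For the omnibus F-tests the excess is at most about 3 points, and only at a correlation of 0.9. Only secondary endpoints are involved. The plan does not hold their joint error at 5% in any case, since it says "unless corrected for multiple testing" without defining a correction.

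All of this stands, and it rules out four stronger conclusions that a reader might draw:
- **That the tests fail their 5% level.** The documents support only that they may, because no correlation is given and silence is not a decision to leave tests uncorrected.
- **That the entry limits on VISA-A and VAS cause the problem.** They do compress T0, but in the range where inflation occurs this moves ε towards 1. Truncation also weakens the correlation with T0, yet ε remains above its untruncated value (0.83 against 0.77 at ρ = 0.8).
- **That the error is 9-13%.** Those rates need a visit-versus-T0 contrast on the pooled ANOVA error. Section 4.15 neither specifies nor excludes one.
- **That VISA-A at T8 is affected.** It is tested by ANCOVA.

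The objection does not remove the gap itself. Tests on three and four time points are planned at a stated level with no safeguard for the condition they rely on, and a standard safeguard is almost free.

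**Conclusion.** The point holds as a modest one about secondary endpoints. Items 1 and 2 of section 4.15, and item 3 where ANOVA is used, lack a sphericity correction or covariance model. For VISA-A and VAS, the uncorrected time and group-by-time F-tests would run at about 5-7% and 5-8% for follow-up correlations of 0.7 to 0.9, with negligible excess at 0.6 or below. Pooled-error contrasts against T0, if used, would run at about 6-9% and 7-13%. No error rate was worked out for SF-12.

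These figures rest on a T0-to-follow-up correlation of 0.447 before truncation, a common follow-up correlation, a VAS SD of 2, normal complete data and 28 per arm. The primary analysis and the stated power are untouched.

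**What to change.** In section 4.15, items 1 and 2, and item 3 where ANOVA is used, replace the repeated-measures ANOVA with a repeated-measures mixed model with unstructured covariance, testing the group difference in change from T0 at each visit. If ANOVA is kept, require the Greenhouse-Geisser correction for every time and group-by-time test, and contrast-specific error terms for each visit-versus-T0 comparison. Leave the primary T8 ANCOVA as it is.

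The cost is one or two sentences and routine software options, with no new data. There are slightly fewer error degrees of freedom, so some p-values become a little larger. In every setting tried, the Greenhouse-Geisser correction kept the error between 4.5% and 5.1%.

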#### 4.15. Plan of statistical analysis

The primary endpoint will be evaluated by Ancova, as described in the numerosity calculation.

Secondary endpoints will be assessed as follows: 1) the VISA-A score at time T3s and T6s/FU compared with time T0 with Anova at repeated measures between group and within group; 2) the VAS at time T3s, T6s/FU and T8s/FU compared with time T0 with Anova at repeated measures between group and within group; 3) the SF12 questionnaire at time T3s, T6s/FU and T8s/FU compared with time T0 with Anova at repeated measures or Friedman's test; 4) the fraction of subjects in each group reaching Minimal Clinical Disease (MCD) considering that the MCD of the VISA-A questionnaire is 18.5 (90% MCD) with Fisher's exact test; 5) the units of analgesic drug consumed according to the clinical diary at time T3s, T6s/FUs and time T8s/FUs (paracetamol 1000 mg will be used as "rescue dose" in case of pain onset/recrudescence) with Friedman's exact test; 6) the fraction of subjects in each group who drop out of the investigation early in relation to Adverse Events (AE/SAE/SUSAR) with Fisher's exact test.

Statistical significance will be assumed for  $p < 0.05$ , unless corrected for multiple testing.

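### Section 4.15 does not say which repeated-measures F-test decides VISA-A (T3, T6) and VAS; if it is the group main effect, the T0 score dilutes the treatment difference.

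*Protocol*

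**What the plan says.** Item 1 of section 4.15 in the Protocol analyses "the VISA-A score at time T3s and T6s/FU compared with time T0 with Anova at repeated measures between group and within group". Item 2 applies the same method to VAS, whose endpoint in the Protocol's secondary end points is "Assessment of the VAS score at time T3w, T6w/FU and T8w/FU compared to time T0". Section 4.15 of the Combined protocol and SAP has the same wording, "with Anova at repeated measures between group and within group".

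Neither document names a deciding F-test for these endpoints. Neither mentions a group-by-time interaction, a change-score contrast, or T0 as a covariate for them. ANCOVA is specified only for the primary endpoint, VISA-A at T8. Section 3.9.1 places T0 before treatment starts.

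**The concern.** A within-group comparison against T0 makes T0 one level of the time factor. The group main effect of that ANOVA is the arm difference averaged over every level, including a visit at which no treatment has been given and the expected difference is zero. If that test decides, a real effect is tested at a fraction of its size.

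The within-group test compares each arm with its own start. Both arms do six weeks of eccentric exercise, so a change from T0 within one arm does not isolate the device.

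Because the deciding test is not fixed, the choice between main effect and interaction is open after the data are seen, and the two tests answer different questions.

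**Working it through.** **Inputs from the documents.** Section 4.14: "A one-covariance analysis for two arms of 28 subjects each"; a covariate of interest that "differs by 12 units in its mean value between the two arms"; "with a common standard deviation assumed to be 15 units"; R² 0.2; "using an F-test at a significance level of 0.05". Section 3.6: VISA-A at entry between 50 and 75.

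**The plan's own figure.** Noncentrality = (28/2) × 12² / (15² × 0.8) = 14 × 144/180 = 11.2. The F-test on 1 and 53 df has power 90.75%, as stated for the primary ANCOVA. The documents give no power for the secondary analyses.

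**Dilution of the main effect.** This step needs no correlation.
- VISA-A over T0, T3, T6, with difference d at both later visits: (0 + d + d)/3 = 2d/3. For d = 12 this is 8 points.
- VAS over T0, T3, T6, T8: (0 + d + d + d)/4 = 3d/4. The documents give no VAS effect or SD, so only the ratio can be shown.

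**Assumptions for power.**
- 12 points at both T3 and T6. The documents give 12 for T8 only.
- Post-baseline SD 15, carried over from section 4.14.
- T0-to-post correlation √0.2 = 0.447, taking T0 as the covariate behind R² 0.2.
- Correlation between T3 and T6 of 0.7, which is not in the documents.
- T0 SD, s, from 7.2 (entry scores roughly uniform: 25/√12) to 12.5 (half of the 25-point entry range, the largest SD that it allows).

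**Main effect.** Variance of the three-visit average = [s² + 2 × 225 + 4 × 0.447 × s × 15 + 2 × 0.7 × 225]/9.
- s = 7.2: variance 112.2 (SD 10.6). Noncentrality = 14 × 8²/112.2 = 7.98. Power 79%.
- s = 12.5: variance 139.6 (SD 11.8). Noncentrality = 14 × 8²/139.6 = 6.42. Power 70%.

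**Baseline-adjusted mean of T3 and T6.** Variance = 225 × (1 + 0.7)/2 − 0.2 × 225 = 191.25 − 45 = 146.25, whatever s is. Noncentrality = 14 × 12²/146.25 = 13.8. Power 95%.

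**Group-by-time interaction.** Simulated, F-test on 2 and 108 df without sphericity correction.

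| Effect at T3 and T6 | T0 SD | Main effect | Interaction | Adjusted for T0 |
|---|---|---|---|---|
| 12 points | 7.2 | 79% | 94% | 95% |
| 12 points | 12.5 | 70% | 90% | 95% |
| 8 points | 7.2 | 46% | about 64% | 68% |
| 8 points | 12.5 | 38% | 57% | 68% |

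**Sensitivity.** With a T3-T6 correlation of 0.447 instead of 0.7 and a 12-point effect, the main effect has 84% (s = 7.2) or 79% (s = 10), against 98% for the adjusted mean.

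**The case against.** The strongest reply concerns the reading. Between and within can simply name the two factors of the design, and comparing arms on scores taken relative to T0 is naturally a comparison of change, which is the interaction. The endpoint wording in section 3.14.1 fits that reading. This stands: a reader might infer that the plan does test 12 points as 8, but the documents do not name the main effect as the deciding test, so the dilution is conditional.

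Other points that stand:
- Read alone, 12 becoming 8 overstates the loss, because averaging also lowers the SD from 15 to 10.6-11.8. The powers above allow for this.
- One might set the T0 SD at 15, like the later visits, and obtain a larger loss. The entry range rules that out.
- The 12 points come from the primary endpoint, where "A difference between the two groups of 12 out of 100 points on the questionnaire can be considered clinically significant". No effect is stated for T3 or T6.
- With a roughly uniform spread of entry scores and 12 points, the interaction loses only about one point of power against adjustment.
- ANCOVA at T8 beside a longitudinal ANOVA at earlier visits might look contradictory. They are different analyses of different visits.
- The plan does not say that a within-group p-value will be presented as a device effect; that is a risk in reporting.
- Classical repeated-measures ANOVA uses complete rows, but missing visits are a separate matter and are not quantified here. Section 4.14 inflates for 20% dropout, and section 3.15 plans a final evaluation of subjects who leave early.

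The reply does not remove the gap itself. The text supports two readings with different power, and adjustment for T0 was at least as powerful as either in every scenario shown.

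**Conclusion.** The point holds as an unnamed deciding test with a conditional loss. Under the main-effect reading, an effect equal at all post-baseline visits is tested at two thirds (VISA-A) or three quarters (VAS) of its size. For 12 VISA-A points, power is 70-79% against 95% with adjustment for T0. Under the interaction reading there is no dilution, and power is 90-94% against the same 95%. The ratios follow from the design. The powers rest on the assumed visit correlations, the T0 SD range and the transfer of 12 points from T8 to T3 and T6.

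The consequence is limited. These endpoints are secondary, and including T0 pulls the main effect towards the null, so it does not create false positives. A reader might infer that the primary result or the sample size is weakened. Neither is: the primary endpoint has its own ANCOVA, and its stated power reproduces.

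**What to change.** In section 4.15, items 1 and 2, of both documents, replace repeated-measures ANOVA with a mixed model, or ANCOVA by visit. Use the post-baseline scores as outcome and the T0 score as covariate, with arm, visit and, in the mixed model, arm-by-visit. Report the between-arm difference with 95% CI at T3 and T6 for VISA-A, and at T3, T6 and T8 for VAS. Leave VISA-A at T8 to the primary ANCOVA, so that the primary endpoint does not acquire a second analysis. Make within-group changes descriptive only.

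If repeated-measures ANOVA is kept, state that the group-by-time interaction decides.

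The cost is wording. Tab. 1 already schedules VISA-A and VAS at T0, T3, T6 and T8, so no visit or measurement is added.

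### Fisher's exact test for the VISA-A responder fraction is valid but conservative at this trial's size; Boschloo's exact test would recover some power at almost no cost

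*Protocol*

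**What the plan says.** The Protocol and the combined protocol and SAP carry the same text for this endpoint. Section 4.15 opens its list with "Secondary endpoints will be assessed as follows". Item 4 then compares the fraction of subjects in each group who reach the VISA-A threshold, "considering that the MCD of the VISA-A questionnaire is 18.5 (90% MCD) with Fisher's exact test". The general significance rule is "Statistical significance will be assumed for $p < 0.05$, unless corrected for multiple testing".

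Section 4.14 bases the trial's size on the primary ANCOVA alone: "two arms of 28 subjects each", "using an F-test at a significance level of 0.05". It then allows for loss: "Assuming dropout patients to be 20% of the total", so that "the inflated sample size of the protocol becomes 36 patients per arm".

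For the responder comparison the documents give no expected rates, power, sidedness or timepoint, and no rule for subjects who drop out. Item 4 includes no baseline adjustment, although section 3.6 admits "Subjects with a VISA A score between 50 and 75".

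**The concern.** Fisher's test conditions on the total number of responders. With about 30 subjects per arm, the conditional distribution has few distinct p-values near 0.05, so the true error rate falls below the nominal 5%. An exact test that does not condition on that total can use more of the allowance while still guaranteeing 5%. If so, the plan gives up power on its patient-level responder result, in a trial of 72 subjects, and gets nothing in return.

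There is a smaller, separate point. If a responder is someone who gains at least 18.5 points, a subject entering at 50 must reach 50 + 18.5 = 68.5, and one entering at 75 must reach 75 + 18.5 = 93.5 out of 100. The unadjusted comparison ignores that difference.

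**Working it through.** **The plan's own figure.** Section 4.14 gives a difference of 12, SD 15, R² 0.2 and 28 per arm. Residual variance = 15² × (1 − 0.2) = 180, so residual SD = 13.42. Noncentrality = (28 × 28 / 56) × 12² / 180 = 11.2. A noncentral F with 1 and 53 df gives 90.75% power, as stated. That figure belongs to the primary ANCOVA; the responder test has none to reproduce.

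**Assumed responder rates.** Assume that a responder gains at least 18.5 points from T0 to T8w, that change scores are normal, and that the control arm gains m points on average:
- control rate = 1 − Φ((18.5 − m)/SD)
- treated rate = 1 − Φ((18.5 − m − 12)/SD)

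With m = 10 and SD 15 these are 1 − Φ(0.567) = 0.285 and 1 − Φ(−0.233) = 0.592, or roughly 30% v 60%. Because m is not in the documents, it was varied from 0 to 20 in steps of 1, with SD 15 and with 13.4.

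**Tests.** All 2×2 tables were enumerated. Size is the rejection probability, maximised over a common response rate. Fisher's test rejects when its two-sided p-value is at most 0.05. Boschloo's test rejects when the Fisher p-value is at most c, where c is the largest cut-off that keeps the maximum size within 5%. That c is 0.0797 at 28/28 and 0.0847 at 36/36. Since c is never below 0.05, Boschloo's rejection region contains Fisher's, and it cannot be less powerful.

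**Power at 30% v 60%.**
- 28/28: Fisher 50.8%, Boschloo 60.7%, gain 9.9 points
- 36/36: Fisher 63.6%, Boschloo 72.2%, gain 8.6 points

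At 20% v 50% and 28/28, power goes from 57.5% to 64.9%, a gain of 7.4 points.

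**Across the assumed rates** (first arm = Group A):

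| Arms | Fisher max size | Boschloo max size | Power gain in points: range (median) |
|---|---|---|---|
| 28/28 | 2.77% | 4.62% | 7.0-12.2 (8.8) |
| 30/30 | 2.74% | 4.69% | 4.2-9.0 (7.2) |
| 32/32 | 3.28% | 4.67% | 1.6-7.8 (6.6) |
| 33/33 | 3.56% | 4.85% | 0.9-9.7 (7.1) |
| 36/36 | 2.79% | 4.94% | 6.6-9.9 (8.1) |
| 28/29 | 3.43% | 4.92% | 2.4-6.8 (5.0) |
| 27/29 | 3.59% | 4.85% | 2.7-8.2 (4.6) |
| 26/30 | 3.74% | 4.98% | 1.7-9.3 (5.6) |
| 30/33 | 4.30% | 4.85% | 0.1-4.9 (2.7) |
| 35/37 | 3.90% | 4.84% | 1.6-6.5 (3.4) |
| 34/38 | 3.93% | 4.93% | 0.5-6.5 (2.9) |

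Which arm is larger also matters. At 30% v 60% with arms of 27 and 29, the gain is 8.1 points if Group A has 27 (53.6% to 61.7%) and 4.9 if it has 29 (57.2% to 62.1%).

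**Why unequal arms are the realistic case.** Section 3.8 uses blocks of 9, and no complete block of 9 can be split equally. Enrolment is competitive across centres, and 20% dropout is assumed.

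**The case against.** The strongest reply is that nothing here is wrong. Fisher's test is standard and holds the error rate below 5%. The choice between conditional and unconditional exact tests is a long-standing matter of preference. The endpoint is secondary, no power is claimed for it, and the same instrument is analysed by ANCOVA as the primary endpoint. All of that stands, and it limits how much weight the point can bear.

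A reader of the equal-arm figures might infer that the plan wastes about half its 5% and loses 9-10 points of power as a general fact. The documents do not support that. An error rate below 3% needs particular equal arm sizes; it is already 3.28% at 32/32 and 3.56% at 33/33. A gain of 9-10 points also needs responder rates that the documents do not give. At 30% v 60% the gain falls to 3.3 points at 32/32 (61.9% to 65.2%) and 2.4 at 33/33 (64.6% to 67.0%).

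On baseline, randomisation protects the unadjusted comparison from bias, and Boschloo's test ignores T0 VISA-A just as Fisher's does. A reader might also expect logistic regression with T0 VISA-A to bring a known gain. A simulation at 28 per arm gave it 65-72% power, but it used an assumed uniform baseline and assumed slopes, and its type I error was 5.1-6.6%. That is not a like-for-like comparison with a test that guarantees 5%.

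What survives is narrower: at every arm size examined, Boschloo's test is at least as powerful, guarantees the same level, and needs no further data.

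**Conclusion.** The point holds as an efficiency improvement, not as a fault in validity. Fisher's test in item 4 is conservative. How conservative depends on final arm sizes that cannot be known in advance, and the power gain also depends on responder rates that are assumed here. It rests on a two-sided 0.05 test, the gain-of-18.5 definition, normal change scores, the plan's 12-point difference, and SD 15 or 13.4.

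The direction is certain, because one rejection region contains the other. The size is not: under these assumptions it runs from about 0 to 12 points. The change is worth making because it costs so little, and it has no bearing on the trial's main conclusion.

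**What to change.** In section 4.15, item 4, of both documents, before outcome data are seen:

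- Replace Fisher's test with Boschloo's unconditional exact test at two-sided 0.05, and report the risk difference with its 95% CI.
- Add, as a supportive analysis only, logistic regression for group with T0 VISA-A as covariate. Claim no specific power gain for it.
- In the same edit, state the timepoint, the responder definition and how dropouts are counted. Changing the test does not settle these.

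The cost is one line of wording for the test and a method that some readers will know less well. It is available in standard software, and no extra subjects, visits or data are needed. The timing matters: chosen after the results are known, the more powerful test would look opportunistic.
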